## 6.2 Exclusion (Eligibility) Criteria

- 1) Greater than 4 cores positive, of any Gleason score, on the UM review,
- 2) Greater than 2 cores positive for Gleason 3+4 cancer,
- 3) Gleason 4+3 or higher cancer in any single biopsy core.
- 4) Extracapsular extension suspected on digital rectal exam with confirmation on MRI. Suspicion of extracapsular extension on MRI alone is not an exclusion for study enrollment.
- 5) Subject is not a candidate for multiparametric MRI with contrast. Some reasons may include (but are not limited to): renal insufficiency, foreign body or pacemakers.
- 6) No prior pelvic radiotherapy
- 7) No prior surgery to the prostate, other than transurethral procedures for benign prostatic hyperplasia (e.g., transurethral resection, green light laser treatment)
- 8) No concurrent, active malignancy, other than non-metastatic skin cancer of any type, superficial bladder cancer, or early stage chronic lymphocytic leukemia (well-differentiated small cell lymphocytic lymphoma) or <stage IV follicular lymphoma. If a prior malignancy is in remission for  $\geq$  3 years then the patient is eligible.
- 9) Bilateral hip replacement.

## 6.3 Gender and Ethnicity

Prostate cancer is a disease of adult men, with exceptionally few diagnosed at 35 years of age. Therefore, women and children are not candidates for this protocol. Based on standard NIH definitions, we estimate that approximately 40% of patients will be White, 24% African American, 35% Hispanic and 1% other at the University of Miami.

# 7. CLINICAL, RADIOLOGICAL AND LABORATORY EVALUATIONS

## 7.1 Screening Evaluations

- History and physical exam, within 12 months prior to protocol enrollment.
- Serum PSA (+/-) 3 months of protocol enrollment.
- Pathology review at the University of Miami of the outside biopsy material, prior to enrollment.

## 7.2 Evaluations During Intervention\*

- Multiparametric MRI obtained at the University of Miami (+/-) 3 months of enrollment and at 12, 24, and 36 months from initial protocol prostate biopsy.

- MRIus-guided biopsies will be obtained at 0 to 3 months from enrollment (“initial biopsy”) and at 12, 24 and 36 month from initial biopsy.
- History and physical at the discretion of the treating physician. Treating physician can be outside of UM..
- Serum PSA will be done preferably every 6 months or at least once a year up to 36 months from the initial biopsy. If the subject progress, PSA should be done every 6 months (+/- 3 months) or at the discretion of the clinician for the first 3 years and then annually thereafter (+/-6 months) for up to 5 years post treatment.
- If possible, plasma and/or serum (up to 5 tubes) for research purposes (biomarkers) may be obtained at 0 to 3 months from enrollment and at 12, 24, and 36 months from initial biopsy (optional - patient may refuse),
- If possible, post prostate-massage urine (approximately 50 mL) may be collected for research purposes at 0 to 3 months from enrollment and at 12, 24, and 36 months from initial biopsy (optional - patient may refuse). Urine research collection will not be done if research funds are not available.
- Quality of Life surveys obtained 0 to 3 months after enrollment and every 12 months from initial biopsy:
  - Expanded Prostate Cancer Index Composite Questionnaire (EPIC+SF12)
  - Memorial Anxiety Scale for Prostate Cancer patients (MAX-PC)
  - Optional - Food Frequency Questionnaire (FFQ) will be collected only atbaseline.

*\* Follow-up evaluations and visits may occur  $\pm$  1.5 months around each scheduled 6-month timepoint. For example, for the 6 month follow-up, the patient may be seen anytime between 4.5 and 7.5 months from the time of the first prostate biopsy. For the 12-month follow-up, the patient may be biopsied between 10.5 and 13.5 months from the time of the first prostate biopsy. Since the first biopsy may be from between 0-6 months from the day the patient is enrolled, each subsequent calendar event is timed in reference to the time of that first biopsy.*

### 7.3 Early discontinuation of study participation

Patients who experience protocol-defined progression will have attained the primary study outcome and will undergo treatment either with radical prostatectomy or whole gland image guided radiotherapy of the prostate at the University of Miami. Their histopathology (for surgery patients) and rates of biochemical recurrence will be followed and compared to historical series for comparison with cohorts not undergoing MRI guided selection for surveillance versus immediate treatment. However, those who refuse the recommendation for treatment will continue to be followed per active surveillance standard of care guidelines. Furthermore, those who seek treatment outside UM will be contacted for information on histopathology (for those undergoing surgery) and rates of biochemical recurrence. Patient refusal of the recommendation for treatment or further follow-up beyond progression will not be a protocol deviation. Patients who are without progression upon completion of the third annual biopsy will be censored without progression.

## 7.4 Multiparametric MRI

Multiparametric MRI exam of the pelvis and prostate, including T2, T1 non-contrast, T1 DCE and DWI MRI scans will be carried out at the GE Discovery MR750 3T MRI unit located at the University of Miami on 3T MRI at the University of Miami. The GE Discovery MR750 3T in the department of Radiation Oncology is preferred, but not mandated. Standard contraindications to MRI, such as ferromagnetic metal in body/eye, pacemaker, defibrillator, other mechanical device, or extreme claustrophobia (medication with anti-anxiety agents, such as Ativan, may be attempted) will prevent eligibility and will be applied for all protocol-related MRIs. Since the DCE-MRI scan involves the use of gadolinium, renal function should be assessed per routine policies.

A preparation procedure protocol has been developed to optimize the multiparametric MRI (see Appendix III) and will be recommended to the patient, but not mandated. A diet designed to reduce bowel gas will also be recommended to begin the day before the diagnostic MP-MRI. This protocol is a guide and slight variations are acceptable. Imaging parameters will be recorded on each patient in the CRFs. As a quality control measure, every MP-MRI will be reviewed by the study team within 45 days for adequacy. If the MP-MRI is deemed inadequate, another MRI will be requested within 30 days. An inadequate exam at that point will be deemed a protocol deviation. De-identified data will be sent to Moffitt Cancer center for radiomics as described below.

## 7.5 Prostate Biopsy

Standard antibiotic prophylaxis of will be at the discretion of the physician managing the biopsy. Aspirin, anticoagulants and vitamin supplements will be temporarily discontinued at least one week prior to the procedure, per routine; these drugs may be restarted per standard practice for prostate biopsies (typically a day or two later if there is no bleeding). The typical and recommended procedure involves placement of the patient in the left lateral decubitus position. Immediately prior to the procedure, 10 cc of 1% Lidocaine may be injected into the periprostatic nerve plexus under ultrasound guidance, typically using a 22 gauge 7-inch needle. The syringe is aspirated before the lidocaine injection to prevent unintentional injection into the vascular compartment. An ultrasonographic wheal may be viewed in the sagittal plane between the rectal wall and base of the seminal vesicles.

Transrectal ultrasound biopsies will be performed on an FDA-approved device using standard techniques. Twelve to fourteen needle core biopsies are desired, but the managing physician may opt for fewer, if there are complications or other indications, or more, if an area of interest was felt to be inadequately biopsied (needle misdirection or other reason). The managing physician will be a co-investigator and will understand the protocol goal of 12-14 cores per prostate biopsy. The arrangement that is recommended (not mandatory) will be left lateral base (LLB), left lateral mid (LLM), left lateral apex (LLA), left medial base (LMB), left medial mid (LMM), left medial apex (LMA), right lateral base (RLB), right lateral mid (RLM), right lateral apex (RLA), right medial base (RMB), right medial mid (RMM) and right medial apex (RMA). Transition zone biopsies may be acquired. The MRPlus biopsies will be performed in the same fashion, but corresponding needle cores will be targeted towards the suspicious areas (see Figure 6). During the course of the procedure, hemorrhage may be visualized within the bladder following needle

biopsy. If this is the case, or if gross blood is noted at the urethral meatus, bladder catheterization and clot irrigation may be indicated, as determined by the urologist.

The procedure will be performed by an urologist in the Department of Urology [name] at the University of Miami. For patients with MRI visible lesions, an MRI-US fusion biopsy will be performed in addition to the standard template (above). MRI-US fusion biopsies will be performed preferably using the Uro-Nav system from Invivo, Philips; although, the Artemis system is available in the department of urology and may be used.

#### *7.5.1 MRI-Ultrasound (MRI-US) Registration for Targeted Prostate Biopsy*

MRI-US fusion biopsy will be performed on an FDA approved platform (e.g., UroNav, In Vivo). The approach begins with multiparametric MRI of the prostate as described above. Expert radiologists will interpret the MRI with the assistance of in-house and/or commercially available software. Suspicious lesions will be determined based on multiple parameters and delineated on the MRI by a panel of expert radiologists with experience reading prostate MRI. Biopsy needle localization and tracking is recorded by an external magnetic field while the biopsy is performed using freehand transrectal ultrasound. Once the MRI is loaded onto the software platform, an initial transrectal ultrasound sweep of the prostate of the prostate is performed, and a rigid image fusion is performed allowing clinicians to see both the MRI and ultrasound images moving together in real time. The lesion on MRI is then targeted using ultrasound to ensure the correct depth and course of the needle to ensure the needle enters the suspicious area. By using freehand ultrasound, a technique familiar to urologists, the learning curve for the procedure is steep and the workflow preserved allowing a quick procedure for the patient.

### **7.6 Biopsy Tissue Handling**

Immediately following each biopsy core, the tissues will be fixed in 10% formalin per routine. The formalin fixed tissues will be delivered to the Department of Pathology for paraffin embedding and sectioning.

The biopsies are to be placed in the tissue processor and processed routinely, and embedded in paraffin. Biopsies will be reviewed by a pathologist and the results (Gleason scoring and percent of tumor tissue) recorded in the patient's record per routine. The remainder of the block will be stored per institutional policy in the Department of Pathology and requests for the biomarker analyses made at a time batched staining is possible (after a number of cases have been accrued).

When the tissue is sectioned for biomarker analyses, the slides will be labeled with a research ID number and will not contain patient information. Biomarker data will be entered into the Active Surveillance Database, which links the patient Medical Record number to a participant's Research ID number and in which data on each patient related to biopsies and treatments will be recorded. De-identified data will be sent to Genome Dx for gene expression profiling as described below.

## **7.7 Molecular Analyses of Blood and Urine**

The objectives are to identify and examine molecular and genomic biomarkers in blood products and the urine that predict for disease progression and see how they correlate with radiomic and genomic signatures from distinct regions of the prostate.

Blood may be collected at baseline, and at 12, 24 and 36 months after initial biopsy. Urine post prostate massage may be collected at baseline and 12, 1,24 and 36 months after initial biopsy. Note that the collection of research fluids is optional – the patient can refuse the procedure. While these are exploratory studies, of key importance is to have such samples collected prospectively on a well-defined group of patients. Any urine or blood that is not used for specific biomarker testing will be stored for biomarkers development or validation.

## **7.8 Quality of Life and/or Outcomes**

Psychosocial assessments will be conducted by a trained and fully-bilingual clinical coordinator/research nurse with experience in conducting psychosocial assessments in prostate cancer populations. We will make every effort to pair our psychosocial assessment visits with scheduled clinic appointments to reduce participant burden. The psychosocial battery will last between 30-40 minutes. All assessments will be conducted in private rooms in our clinics. All psychosocial data will be de-identified and only coded by participant number. Should a participant display any significant signs of distress (e.g., high levels of anxiety, depressed mood or spontaneous comments suggesting a need for psychosocial care), we will refer participants to appropriate psychosocial resources within our medical center.

## **7.9 Treatment**

Men undergoing protocol defined progression will undergo for radical prostatectomy, prostate dose escalated (EQD2 >78Gy) image guided radiotherapy of the prostate, HiFu or any other prostate treatment. Although patients will be encouraged to seek treatment at the University of Miami to continue follow up on trial, we understand that patients may select to be treated elsewhere and this would not be considered a deviation from the protocol. Both treatment modalities are offered at the University of Miami and portend excellent cancer control in men with localized tumors. Patients will be counseled regarding with risks and benefits of both approach's to allow for informed decision-making between the two options. Men undergoing surgery will have their pathology specimen compared to men in the University of Miami active surveillance database who had surgery after initial surveillance without MRI. After surgery men will be followed every 3-6 months (+/- 2 months) for the first year, every 6-12 months (+/- 3 months) in the second year, and annually (+/- 6 months) thereafter up to 5 years post surgery. Any adjustments to this schedule will be permitted under the discretion of the clinician. A PSA of 0.2 ng/ml with a repeat value showing the same or higher will be used to define biochemical recurrence post radical prostatectomy. For men undergoing radiation therapy, the method and dose of radiation that will be delivered will be left to the discretion of the treating physician. For men undergoing radiotherapy of the prostate, follow up serum PSA testing should occur every 6 months (+/- 3 months) for the first 3 years and then annually thereafter (+/- 6 months) for up to 5 years post treatment. A PSA of 2 ng/ml above the nadir will be used to define biochemical failure post radiation.

Rates of biochemical recurrence post-surgery or radiation will be compared to historical data of men being treated after initial surveillance at the University of Miami. Androgen deprivation will be prescribed at the discretion of the treating physician. Men who decline treatment despite progression and recommendation for treatment will be followed as per standard of care active surveillance criteria. Men who desire to undergo their treatments at centers outside the University of Miami will be contacted to attain post treatment oncologic data, as described above. Patient refusal to undergo treatment based on the protocol will be followed as per the treated physician. If the patient chose to seek treatment elsewhere will be left to the clinician and patients discretion and will not be considered a deviation of the protocol.

If the patient enters a radiation oncology clinical trial, then the timing of PSA and other labs will be timed in accordance with the radiation treatment protocol.

## **8. ADVERSE EVENT REPORTING**

During the active surveillance part of the study, the only difference is the addition of a multiparametric MRI and MRI-US fusion biopsies in addition to random biopsy. The only adverse events expected from obtaining an MRI would include allergic reaction to the contrast, renal toxicity, or claustrophobia. Other than guidance by MRI, the prostate biopsy will be performed in the same fashion as standard biopsy of the prostate and therefore carries no increased risk from bleeding or infection. The addition of MRI guided biopsy has not been shown to increase the risk of infection or bleeding, compared to random biopsies alone. These procedures are standardized and the risks well-documented. In the unlikely event that a study patient experiences an adverse reaction to a study related procedure, this will be reported to the University of Miami Institutional Review Board as per their policies and using the grading scales of the NIH CTCAE version 4.0.

If the patient progress and decide to undergo either radical prostatectomy or radiotherapy or any other procedure:

### *8.2.1 Recording Abnormal Findings*

In any clinical assessment, a value outside the normal or reference range (such as a clinical laboratory, vital signs, imaging findings or EKG findings) will not be recorded or assessed as an adverse event unless that value is considered to be of clinical significance by the investigator

### *8.2.2 Recording Signs and Symptoms*

Sign, symptoms, or procedures resulting from an underlying clinical diagnosis should be documented as one comprehensive adverse event. If no underlying clinical diagnosis can be identified, each sign and symptom should be recorded as a separate independent event.

However, a new or worsening event resulting from an underlying clinical diagnosis or a reaction to concurrent medications should be documented as a separate independent adverse event unless it is within the normal range of fluctuation for that patient.

### **8.2.3 Recording Grade Changes**

Adverse events will be recorded at the maximum grade/severity experienced for the duration of the event. Should one particular AE warrant further investigation, additional details may be collected at the discretion of the adverse event;

### **8.2.4 Reporting Period**

Adverse Events relating to radical prostatectomy and radiotherapy that are not related to MRI or MR biopsy, will not be documented in the adverse event log. Concomitant medication will not be recorded after the subject progress.

### **8.2.5 IRB Reporting**

All adverse events that are serious adverse events **and** are unexpected **and** are related or possibly related IRB within ten (10) working days of being made known to the Principal Investigator. Events that are more frequent than anticipated or more severe than expected must be reported to the IRB within ten (10) working days of being made known to the Principal Investigator.

All **unanticipated** deaths or life-threatening problems suspected as being a direct outcome or possibly an outcome of the study intervention must be reported to the IRB within 24 hours of being made known to the Principal Investigator.

For all SAE's, the investigator is obligated to pursue and provide follow-up reporting information until the event has resolved or until an acceptable medical endpoint has been reached or the patient is lost to follow-up.

## **9. DATA AND SAFETY MONITORING PLAN**

The study investigators will report to the Sylvester Comprehensive Cancer Center Data and Safety Monitoring Committee (DSMC) to ensure data quality and subject safety. The investigators will conduct continuous reviews of the data and subject safety, keeping track of the number of subjects, significant toxicities in accordance with the protocol and observed responses, which will be discussed at DSMC committee meetings. All grade 3-5 adverse events will be entered into Velos and reviewed at DMSC meetings. In addition, all adverse reactions considered "serious" will be entered into Velos and reviewed by the DSMC on an ongoing basis. If an increase in the frequency of grade 3 or 4 adverse events is noted in the study, a report will be submitted to the DSMC at the time the increased rate is identified. If at any time the principal investigator stops enrollment or stops the study due to safety issues, the DSMC chair and manager will be notified within 1 business day and a formal letter will be sent to the DSMC to be received within 10 business.

## **10. STATISTICAL CONSIDERATIONS**

This is a single-arm trial with the primary objective of determining the rate of progression over 2 years in men undergoing AS who are managed with multiparametric-

MRI and MRI-US fusion prostate biopsies, as compared to historical controls. The primary study endpoint is the 24-month cumulative progression rate based on biopsy criteria.

## 10.1 Primary Study Endpoints

### 10.1.1 Progression

The main study endpoint will be the 24-month cumulative progression rate. In the context of this trial, progression refers to a repeat surveillance biopsy indicating any one of the following: (i) more than 4 positive cores involving any grade of cancer, (ii) three or more cores with Gleason 3+4 cancer, (iii) any single core with Gleason 4+3 cancer or higher, (iv) a Gleason 3+3 at diagnosis that is upgraded to Gleason 3+4 or (v) undergoing treatment, regardless of histological progression. Although many existing active surveillance protocols incorporate volume of cancer in their definition of progression, these are based on random biopsy of the prostate. Critical volumes of cancer based on targeted biopsy have not been defined and will be explored in this analysis.

- Progression rate will be estimated for each scheduled surveillance biopsy as the proportion of study patients without prior progression for whom the biopsy indicates progression.
- Cumulative progression rate will be estimated for each of the four planned biopsies as the proportion of patients with progression among those having had all planned biopsies to date, or a previous biopsy indicating progression.

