### 10.1.2 Histological progression

In the context of this trial, histological progression refers to a surveillance biopsy that indicates any one of the following: (i) more than 4 positive cores involving any grade of cancer, (ii) three or more cores with Gleason 3+4 cancer, (iii) a Gleason 3+3 at diagnosis that is upgrade to Gleason 3+4, or (iv) any single core with Gleason 4+3 cancer or higher.

- Histological progression rate will be estimated for each scheduled biopsy as the proportion of study patients without prior GS progression for whom the biopsy indicates GS progression.
- Cumulative histological progression rate will be estimated for each scheduled biopsy as the proportion of patients with histological progression among those having had all planned biopsies to date, or a previous biopsy indicating Gleason score progression.

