### **10.4 Sample size, accrual rate and study duration**

We plan to accrue approximately 55 patients per year for the first three years of the study; this assumes a 10% dropout rate. The power (97.3%), is based on 150 patients, using a two-sided binomial test at the 5% significance level to detect an increase in the 24-month cumulative progression rate from 12.5%, as expected for AS historically, to 25% for MRI-AS. Enrollment will occur during the first 3.25 years. Enrollment will be completed at < 3.33 years from the enrollment of the last patient.

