## 10.5 Statistical Analysis

Descriptive statistics will be done for patient demographics and baseline disease characteristics. Counts and percentages will be used to summarize the distribution of categorical variables while median, range, mean and standard deviation will be used for continuous variables. Baseline characteristics will include age, race/ethnicity, T-stage, Gleason score, PSA, PSAD and performance status. Continuous scores will be compared using ANOVA and linear regression controlling for common demographic and clinical variables.

For each scheduled surveillance biopsy session, we will tabulate patients and the following status categories: biopsy indicating progression, biopsy negative for progression, biopsy not performed for progression detected on earlier biopsy, biopsy not performed because patient refused, or biopsy not performed because patient dropped out of study.

Time to event endpoints such as progression and BCR will be analyzed by Kaplan-Meier (KM) or competing risk (CR) methods. Where the Kaplan Meier method is used, point estimates and two-sided 95% confidence intervals for rates will be reported for selected times using Greenwood's variance and the log-log transform method. Median survival time, if attained, will also be reported. We will report the progression rate and the cumulative progression rate for each surveillance biopsy. Taking the third scheduled biopsy at the end of 2 years as illustration, the progression rate at 24 months is the proportion of biopsied patients indicating progression among the total number of biopsied patients over the 24 month period. The 24-month cumulative progression rate is the primary endpoint, which will include those who complete the first three biopsies or have progression from the first or second biopsy. The primary endpoint, 24-month cumulative progression rate, will be estimated and reported with corresponding 95% confidence intervals. Groups will be compared by the log rank test. In addition, we will report and plot the cumulative progression rates in each arm for the four scheduled surveillance biopsies. It is expected that the early difference with historical values and those obtained with MRI-guided biopsies will not be sustained; that is, the 36-month cumulative progression rates will be approximately equal. Similar estimation of time-specific and cumulative rates will be done for Histological progression.

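### The 12.5% null has no stated source, event definition or biopsy count and does not match the centre's own cumulative figures; separately, the rule counting treatment as progression does not fit the stated denominators.

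*Combined protocol and SAP*

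**What the plan says.** **The null.** Section 10.4 plans a two-sided binomial test at 5% in 150 patients, with 97.3% power to detect a rise in the 24-month cumulative progression rate "from 12.5%, as expected for AS historically, to 25% for MRI-AS". No citation, cohort, event criteria or biopsy count accompanies the 12.5%. Section 3.1 speaks of the first two non-diagnostic biopsies. Section 10.5 counts three biopsies by 24 months.

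**The centre's history.** Section 1.5.1 reports progression in 7%, 18% and 17% at the first, second and third surveillance biopsies. Overall, 64 of 249 men (26%) progressed over a mean follow-up of 2.9 years, and 61 of the 64 were treated.

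**The event.** Section 10 states: "The primary study endpoint is the 24-month cumulative progression rate based on biopsy criteria". Section 10.1.1 says "progression refers to a repeat surveillance biopsy indicating any one of the following" and includes as item (v) "undergoing treatment, regardless of histological progression". Section 10.1.2 repeats the four biopsy criteria without (v): "histological progression refers to a surveillance biopsy that indicates any one of the following". Section 3.1 glosses progression as conversion to treatment.

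**The denominator.** The cumulative rate is taken "among those having had all planned biopsies to date, or a previous biopsy indicating progression" (10.1.1). Section 10.5 describes the primary endpoint as one "which will include those who complete the first three biopsies or have progression from the first or second biopsy". The status categories in 10.5 include "biopsy not performed for progression detected on earlier biopsy, biopsy not performed because patient refused" and dropout, but none for a man treated without biopsy progression.

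**The concern.** In a single-arm trial the historical rate is the whole comparator. If 12.5% is not the rate that standard biopsy would give under the tested event definition, biopsy count and eligibility, a rejection need not mean that MRI guidance found more progression. Nothing in the plan lets a reader check the match, and the only cohort described in detail gives a higher figure once its per-biopsy rates are accumulated.

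The second gap concerns the numerator and denominator. A man treated without biopsy progression before his third biopsy is an event under (v), yet he has neither all planned biopsies nor an earlier biopsy showing progression. Read literally, the denominators exclude him. Read through the lead-in of 10.1.1, which lists (v) among the things that define progression, he is counted. The plan does not fix the choice, so it could be made after the data are seen. Whether counting him is fair also depends on whether the 12.5% includes treatment, which is not stated.

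**Working it through.** **Inputs.** n = 150, null 12.5%, target 25%, two-sided 5% (10.4). Per-biopsy rates 7%, 18%, 17%; 64 of 249 progressed, 61 of them treated (1.5.1).

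**1. The plan's power.** Exact binomial with at most 2.5% in the upper tail: P(X ≥ 27 | 12.5%) = 0.0325 and P(X ≥ 28 | 12.5%) = 0.0193, so the rule rejects for an increase at 28 or more. P(X ≥ 28 | 25%) = 0.9734. This reproduces 97.3%; the power arithmetic is right.

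**2. The centre's figures as a cumulative rate.** Assume that each rate is conditional on no earlier progression.
- Two re-biopsies: 1 − 0.93 × 0.82 = 0.237.
- Three re-biopsies: 1 − 0.93 × 0.82 × 0.83 = 0.367.

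Neither is near 12.5%. The simple mean of the first two, (7 + 18)/2, is 12.5, but a mean of sequential rates is not a cumulative rate.

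**3. Effect of a wrong null.** Keep the rule of 28 or more of 150 and suppose that MRI adds nothing. The last column re-sets the test to the rate in the first column.

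| True historical rate | Chance of rejecting 12.5% | Power for 25% if this rate were the null |
|---|---|---|
| 12.5% | 1.9% | 97.3% |
| 15% | 12.8% | 87.2% |
| 20% | 69.0% | 28.3% |
| 23.7% | 94.3% | 5.7% |

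**4. How common treatment without progression might be.** The documents give no rate. Section 1.5.1 mentions no treated man other than the 61 progressors. Reading that silence as none gives 0 of 249 − 64 = 185, with exact 95% upper limit 1 − 0.025^(1/185) = 2.0%, over a mean of 2.9 years.

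**5. Effect of the reading at 2%.** Assume that 12.5% excludes treatment, that MRI has no effect, and that 2% of non-progressors are treated before completing biopsies, unrelated to MRI.
- Counted: rate = 1 − 0.875 × 0.98 = 0.1425; P(X ≥ 28 of 150) = 0.080.
- Left out: rate = 0.125/(0.125 + 0.875 × 0.98) = 0.1272; n = 150 × 0.9825 ≈ 147; cut-off still 28; P = 0.019.

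If 12.5% already includes treatment, counting keeps 1.9% and 97.3%. Leaving men out when the composite rate is 25% gives biopsy progression of 1 − 0.75/0.98 = 0.2347. About 2.3 men are dropped, so n = 148, and the rate is 0.2347/(0.2347 + 0.7653 × 0.98) = 0.2383. Power is then 93.6%.

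**The case against.** **On the null.** A reader might infer that the 12.5% has no time window. It has one: 10.4 labels it a 24-month cumulative rate. A reader might also infer that the true historical rate is 23.7% and that the trial has almost no power. The documents do not support that. Section 1.5.1 gives no biopsy timing, so 23.7% is not shown to be a 24-month figure. The conditional reading is an assumption. The cohort met narrower criteria (Gleason 6 or less, at most two cores) than 6.2 allows. Nor do the documents say that 12.5% was obtained by averaging 7% and 18%. What stands is that the null cannot be verified and that the one available comparison does not support it.

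**On the event.** Section 10.1.1 is plainly the operative definition. Section 10 can be read as a summary and 3.1 as a gloss, and the contrast with 10.1.2 suggests that (v) was added on purpose. Only men treated before completing their planned biopsies are affected; a man treated after his third biopsy stays in. Kaplan-Meier or competing-risk analysis and separate histological progression rates are already planned in 10.5. All of this stands and makes the second gap minor.

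It is tempting to say that two men can decide the trial: 28/150 gives exact two-sided p = 0.026, and 26/148 gives p = 0.080. That is a chosen case near the cut-off. It also uses a different rejection rule, since 27/150 already gives p = 0.048 by that method. Simulating n = 150 with 2% of non-progressors treated, the two readings disagree in about 6% of trials at 12.5% biopsy progression, 18% at 18% and 1.4% at 25%. Treatment prompted by MRI may also be part of the intended effect under 3.1, which step 5 does not cover.

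**Conclusion.** The concern holds in two parts of unequal weight.

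The first part should be fixed. The null is labelled as a 24-month cumulative rate but has no stated source, historical event definition or biopsy count, and it disagrees with the accumulated rates of 1.5.1. The consequence is steep: at a true historical rate of 15% the nominal upper-tail error of 1.9% becomes 12.8%, and at 20% it becomes 69%. These are sensitivity figures, not estimates of the actual historical rate.

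The second part is a wording conflict, probably of small effect. If treatment without progression is as rare as 1.5.1 suggests, at most about 2%, the chance of a false increase is 8% or 1.9% depending on the reading, when the null excludes treatment. The 2% limit rests on reading silence in 1.5.1 as zero. The reason to settle it is that the reading is otherwise open once the data are known.

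**What to change.** **Null.** State the source, event definition, number of biopsies and window behind the historical rate. Derive it from the University of Miami active surveillance database under the same event definition, biopsy count (settling two against three) and 24-month window as the tested endpoint. Use overlapping eligibility where records allow, and otherwise state the limitation. Then restate the null and the power.

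**Event and denominator.** Align 3.1, 10 and 10.1.1 on one definition. If (v) stays, say that men treated without histological progression count in both numerator and denominator even when later biopsies are missing, and add a status category for them in 10.5. Report the histological progression rate already planned in 10.5 against a histological historical rate, as a named supporting analysis.

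**Cost.** The second change is a few sentences. The first needs some re-coding of historical records, and the documents do not show that the database holds every field. It may leave a smaller comparison set and probably a less favourable stated power.
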